3.1.3 Double-blind induction period (Week 12 dose through Week 15 dose)

All subjects who complete the Double-blind Treatment Period will enter the Double-blind Induction Period.

During the Double-blind Induction Period, subjects randomized to placebo during the Double-blind Treatment Period will be switched over to treatment with secukinumab 300 mg. The Double-blind Induction Period is defined as the Week 12 dose through the Week 15 dose. **Subjects must administer the Week 12 dose no later than 7 days after the Week 12 FDG-PET/CT scan.**

- **Secukinumab:** Subjects who were randomized to the secukinumab treatment group at Visit 2/Baseline will continue to self-administer secukinumab 300 mg (two s.c. injections of the 150 mg dose) at Week 12. In order to maintain the blind, these subjects will undergo a sham induction with weekly placebo injections at Weeks 13, 14, and 15.
- **Placebo:** Subjects who were randomized to the placebo treatment group at Visit 2/Baseline will begin to self-administer secukinumab 300 mg (two s.c. injections of the secukinumab 150 mg dose) weekly for four weeks at Weeks 12, 13, 14, and 15.

Self-administration of the Week 12 dose will take place at the study site, while the doses at Weeks 13, 14, and 15 will be self-administered at home.

All subjects who discontinue study treatment prematurely for any reason before the end of Double-blind Induction Period should return to the study site for the performance of the Visit 14/Week 52 End of Treatment 2 (EOT2) assessments. The EOT2 visit should be scheduled 28 days (± 7 days) after the last dose of study treatment.

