3.1.4 Open-label treatment period (Week 16 through Week 52)

[figure not shown]
All subjects who complete the Double-blind Induction Period will enter the Open-label Treatment Period. The Open-label Treatment Period is defined as Week 16 through Week 52. All subjects in

the Open-label Treatment Period will receive secukinumab 300 mg s.c. at four-week intervals beginning at Week 16 through Week 48 (last dose during the Open-Label Treatment Period).

Self-administration of the doses at Weeks 16, 24, 32, 40, and 48 will take place at the study site; the doses at Weeks 20, 28, 36, and 44 will be self-administered at home.

All subjects who discontinue study treatment prematurely for any reason before the end of the Open-label Treatment Period should return to the study site for the performance of the Visit 14/Week 52 End of Treatment 2 (EOT2) assessments. The EOT2 visit should be scheduled 28 days (± 7 days) after the last dose of study treatment.

Figure 3-1 Study design

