5.2 Treatment groups

At Visit 2/Baseline, eligible subjects will be randomized to one of the following two treatment groups in a ratio of 1:1, with approximately 42 subjects per group:

1. **Secukinumab group:** Subjects (or trained caregivers) will self-administer (or administer to the subject) a dose of secukinumab 300 mg s.c. (two injections of the 150 mg prefilled

syringes) once weekly for five weeks (at Randomization, Weeks 1, 2, 3, and 4), followed by dosing every four weeks, starting at Week 8 through Week 48. In order to maintain the blinding during the Double-blind Induction Period, placebo s.c. doses (two injections of the placebo to 150 mg prefilled syringe) will be self-administered by the subjects (or trained caregivers) at Weeks 13, 14 and 15.

2. **Placebo group:** Subjects (or trained caregivers) will self-administer (or administer to the subject) a dose of placebo s.c. (two injections of the placebo prefilled syringes) once weekly for five weeks (at Randomization, Weeks 1, 2, 3, and 4), followed by a dose after four weeks at Week 8.

Beginning at Week 12, all subjects in the placebo group will be switched to treatment with secukinumab 300 mg s.c. Subjects will receive a dose of secukinumab 300 mg s.c. once weekly for five weeks (at Weeks 12, 13, 14, 15, and 16) followed by dosing every four weeks, starting at Week 20 through Week 48.

All subjects who enter the Double-blind Induction Period will self-administer the Week 12 dose following the completion of all assessments scheduled to be performed at Visit 8/Week 12 (Table 6-1).

The treatment groups and dosing frequency are also described in Table 5-1 below.

Table 5-1 Overview of study treatment

Treatment group	DB Treatment Period (Rand – Wk 12 pre-dose)	DB Induction Period (Wk 12 – Wk 15)	OL Treatment Period (Wk 16 – Wk 52)
Secukinumab 300 mg	2x s.c. secukinumab 150 mg injection at Rand, Wks 1, 2, 3, 4 and 8	2x s.c. secukinumab 150 mg injection at Wk 12 2x s.c. secukinumab 150 mg PBO injection at Wks 13, 14 and 15	2x s.c. secukinumab 150 mg injection at Wks 16 - 48
Placebo (PBO)	2x s.c. secukinumab 150 mg PBO injection at Rand, Wks 1, 2, 3, 4 and 8	2x s.c. secukinumab 150 mg injection at Wks 12, 13, 14, and 15	2x s.c. secukinumab 150 mg injection at Wks 16 – 48

DB = Double-blind; OL = Open-label; Rand = Randomization; Wk = Week

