5.5.4 Instructions for prescribing and taking study treatment

Throughout the duration of the study, all doses of study treatment (secukinumab 300 mg and placebo) will be self-administered subcutaneously (s.c.) by the subject (or trained caregiver) after all study assessments for each visit have been completed. The prefilled syringes will be provided by the site staff to the subject, who will then self-inject the study treatment. Site staff should remove the assigned study treatment from the refrigerator and allow the syringes to reach room temperature in their unopened box (approximately 15-30 minutes) before self-injection by the subject.

All self-injections during the Double-blind Treatment Period will take place **at the study site**; during the Double-blind Induction and Open-label Treatment periods, self-injections will occur both at the study site and at home. Instructions on the self-administration of the study treatment and disposal of used prefilled syringes are detailed in the secukinumab Instructions For Use (IFU) document and will be provided to each subject.

At the beginning of the study, the Investigator/qualified site staff will determine if self-administration is appropriate for the subject, e.g., manual dexterity, ability to follow the IFU. If a subject requires a caregiver to administer study treatment, the caregiver will be trained by the Investigator/qualified site staff. If a caregiver is not available at a particular visit or the subject is having problems with self-administration, the Investigator/qualified site staff may administer the study treatment to the subject.

A different body site should be chosen each time a dose is administered. Study treatment should not be injected into areas where the skin is tender, bruised, red, scaly or hard, or in an area of skin affected by psoriasis. Areas with scars or stretch marks should be avoided. As far as possible, the injection site should be changed from administration to administration throughout the study. Subjects should self-administer the study treatment to one of the following body regions, changing the injection site routinely: the front of the thighs, the lower stomach area (abdomen) but **not** the area two inches around the navel. In cases where a caregiver will administer the study treatment, the upper outer arms may also be used as an injection site.

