5.5.14 Early study termination

The study can be terminated at any time for any reason by Novartis. Should this be necessary, the subject should be seen as soon as possible and treated as a prematurely withdrawn subject (as described in [Section 5.5.9](#)). The Investigator may be informed of additional procedures to be followed in order to ensure that adequate consideration is given to the protection of the subject's interests. The Investigator will be responsible for informing the Institutional Review Board/Independent Ethics Committee (IRBs/IECs) of the early termination of the trial.

6 Visit schedule and assessments

[Table 6-1](#) lists all of the assessments and indicates with an "X" when the assessments are to be performed.

Subjects should be seen for all visits on the designated day or as close as possible to the original planned visit schedule (recommended visit windows are in [Table 6-1](#). Every effort should be made to respect the time frame for the Visit 8/Week 12 visit.

At a minimum, subjects will be contacted for safety evaluations during the 30 days following the last study visit, including a final contact at the 30-day point. Documentation of attempts to contact the subject should be recorded in the source documentation.

Visit windows

A "visit window" will be allowed during the study as follows:

- Screening Period
 - +2 days (for a total of up to 30 days)
- Double-blind Treatment Period
 - ± 2 days for Visits 3-8
- Open-label Treatment Period
 - ± 7 days for Visits 9-14

Rescreening

Rescreening may be allowed under certain conditions. Requests from the Investigator/site staff to rescreen subjects will be handled on a case-by-case basis with Medical Monitor approval required before proceeding with the rescreening. Rescreening cannot be done if a subject was previously randomized into the study.

If a subject rescreens for the study, the subject must sign a new ICF and be issued a new subject number. The date of the new informed consent signature should correspond to the new subject number. Informed consent for a rescreened subject must be obtained prior to performing study-related assessments or collecting any data for the Screening Visit. For rescreening, all

screening assessments must be performed as per protocol, except for the tuberculosis (TB) work up, if applicable, if performed not more than 12 weeks before randomization.

[figure not shown]

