Fasting labs: plasma glucose	X																					
Viral serology lab analysis: HIV, Hepatitis B and C ^G	X																					X ^d
QuantiFERON [®] TB-Gold In-Tube test ^{G,H}	X																					X ^d
Serum pregnancy test ^{G,I}	X																					X ^d
Urine pregnancy test (local) ^J		X						X													X	X ^d
FDG-PET CT ^K		X ^L						X ^M													X	
Blood sample for cardio-metabolic biomarkers ^G		X [*]				X	X	X [*]						X			X				X [*]	
PASI	X	X				X	X	X				X		X		X		X		X	X	X ^d
IGA mod 2011	X	X				X	X	X				X		X		X		X		X	X	X ^d
Alcohol use assessment			X	X	X	X	X	X				X		X		X		X		X	X	X ^d
DLQI		X						X						X		X		X		X	X	

Period	SCR	Double-blind Treatment Period							Double-blind Induction Period			Open-label Treatment Period								Unscheduled Visit ^D		
		1	2	3	4	5	6	7	8 / EOT1 _{A,B}				9	10		11		12			13	14 / EOT2 _C
Visit	1	2	3	4	5	6	7	8 / EOT1 _{A,B}				9	10		11		12		13	14 / EOT2 _C		
Week	-4 to BL ^E	BL	1	2	3	4	8	12	13	14	15	16	20	24	28	32	36	40	44	48	52	
Visit window (Days)			±2	±2	±2	±2	±2	±2				±7		±7		±7		±7		±7	±7	
Assessment																						
AE/SAE assessment ^N	X	X	X	X	X	X	X	X				X		X		X		X		X	X	X
Randomization via IRT		X																				
Subject self-administration of study treatment at site		X	X	X	X	X	X	X				X		X		X		X		X		
Dispense study treatment to subject for at-home dosing								X				X		X		X		X				
Subject self-administration of study treatment at home and completion of Self-Administration Log ^O										X	X	X		X		X		X		X		
At-home Dosing Phone Reminder ^{F,P}										X			X		X		X		X			
Check Self-Administration Log and returned used/unused study treatment and packaging ^{F,Q}												X		X		X		X		X		X ^d

AE=adverse event; BL = Baseline; DLQI=Dermatology Life Quality Index; EOT1=End of Treatment 1; EOT2=End of Treatment 2; FDG-PET CT=18-fluorodeoxyglucose positron emission tomography with computer assisted tomography; HIV=human immunodeficiency virus; IGA=Investigator's Global Assessment; IRT=Interactive Response Technology; PASI=Psoriasis Area and Severity Index; SAE=Serious Adverse Event; SCR=Screening; TB=tuberculosis

* At Visits 2, 8, and 14, subjects are required to be fasting for a minimum of 8 hours prior to the blood sample collection for cardiometabolic biomarkers

Period	SCR	Double-blind Treatment Period							Double-blind Induction Period			Open-label Treatment Period								Unscheduled Visit ^D		
		1	2	3	4	5	6	7	8 / EOT1 A,B				9		10		11		12			13
Visit	1																					

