^K The FDG-PET/CT scan will be performed at each site’s local imaging center. A clinical reading scan report will be provided to the site within 24 hours of the scan by the local imaging center.

Period	SCR	Double-blind Treatment Period							Double-blind Induction Period			Open-label Treatment Period								Unscheduled Visit ^D		
		1	2	3	4	5	6	7	8 / EOT1 A,B				9		10		11		12			13
Visit	1																					
Week	-4 to BL ^E	BL	1	2	3	4	8	12	13	14	15	16	20	24	28	32	36	40	44	48	52	
Visit window (Days)			±2	±2	±2	±2	±2	±2				±7		±7		±7		±7		±7	±7	
Assessment																						

^L The Visit 2/Baseline FDG-PET/CT scan report must have been reviewed with no clinically significant findings prior to randomization and administration of the initial dose of study treatment (see [Section 3.1.1.1](#) for additional information). Randomization must occur 7 days or less from date of FDG-PET/CT scan.

[figure not shown]
^M The Visit 8/Week 12 FDG-PET/CT must have been reviewed with no clinically significant findings prior to the administration of the Visit 8/Week 12 dose (see [Section 3.1.2.1](#) for additional information). Subjects must administer their Week 12 dose 7 days or less from the date of their Week 12 FDG-PET/CT scan.

^N AE/SAE assessment includes injection site reactions

^O Subjects will self-administer study treatment at home at these time points and will record each dose administered at home in their Self-Administration Dosing Log

^P Site staff to contact subject via telephone to assess subject compliance with at-home dosing and completion of Self-Administration Log

^Q The at-home administrations of study treatment will be recorded by the subject on the Self-Administration Log which must be returned to the site at the next visit along with the used/unused study treatment and the outer boxes for a compliance check.

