6.3 Treatment exposure and compliance

All administered doses of secukinumab or placebo will be recorded on the Dosage Administration Record eCRF. Compliance will be assessed by Novartis and CRO study personnel using the Dosage Administration Record eCRF, medication numbers, Drug Label Form information, and information collected by IRT.

Subjects will be provided with a Self-Administration Log at Visit 8/Week 12 to record the date and time of all at-home study treatment administrations during the Double-blind Induction and Open-label Treatment Periods. Subjects will be instructed to return to the study site at each scheduled visit with their completed Self-Administration Log, where the dosing information will be transcribed by site staff into the Dosage Administration Record eCRF. Subjects will also be instructed to return all used/unused study treatment and packaging to the study site at each visit as part of the compliance check. At the final study visit (Visit 14/Week 52), the subject's Self-Administration Log will be retained in the subject's source documents.

The Investigator/qualified site staff should promote compliance by instructing subjects to attend the study visits as scheduled, to take the study treatments exactly as prescribed, and by reiterating that compliance is necessary for subject safety and the validity of the study. Additionally, sites will be instructed to contact subjects via telephone at the time of scheduled at-home dosing to check compliance and to ensure completion of the Self-Administration Log. Likewise, subjects should be instructed to contact the Investigator/qualified site staff if he/she is unable for any reason to attend a study visit as scheduled, or if he/she is unable for any reason to take the study treatment at home as prescribed.

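### Between Weeks 12 and 52 adverse events are asked about only at site visits 4 to 8 weeks apart; the calls already planned for home dosing could ask as well

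*Protocol*

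**What the plan says.** Protocol Section 7.1 ties active AE questioning to visits. After Week 12 the AE/SAE row of Table 6-1 is marked at Weeks 16, 24, 32, 40, 48 and 52 and at unscheduled visits.

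Dosing is more frequent than that. In the induction period, Section 3.1.3 states that "the doses at Weeks 13, 14, and 15 will be self-administered at home". In the open-label period, Section 3.1.4 states that "the doses at Weeks 20, 28, 36, and 44 will be self-administered at home". For subjects who switch from placebo, all seven of these home doses are active. For subjects on secukinumab from the start, the three in Weeks 13-15 are placebo.

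Table 6-1 also has a row named "At-home Dosing Phone Reminder", explained in footnote P: "Site staff to contact subject via telephone to assess subject compliance with at-home dosing and completion of Self-Administration Log". Section 6.3 says that "sites will be instructed to contact subjects via telephone at the time of scheduled at-home dosing to check compliance" and to see that the log is completed. Neither place mentions AEs or new medications.

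Section 6.5 asks that AE evaluation, including injection site reactions, be repeated after a dose. Section 6 also provides for safety contact during the 30 days after the last study visit.

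**The concern.** Placebo switchers have their first secukinumab exposure in Weeks 12-15. All subjects are asked about AEs weekly through Weeks 0-4, when the original secukinumab arm has its induction. The switchers are asked at Week 12, before their first active dose, and next at Week 16. In the open-label period one scheduled question covers eight weeks.

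Protocol Section 3.6 names infection and hypersensitivity among the drug's risks and relies on close clinical monitoring to limit risk. Longer-term safety is one reason given in Section 3.2 for the 52-week duration, and Section 8.4 requires no data monitoring committee. What is at stake is how long subjects must recall events, and how soon a site hears of events that a subject does not volunteer. The site already plans to speak to the subject in these gaps, but on another subject.

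**Working it through.** **Inputs.** AE-marked weeks from Week 12 on: 12, 16, 24, 32, 40, 48, 52 (Table 6-1). Home doses: Weeks 13, 14, 15, 20, 28, 36, 44 (Sections 3.1.3 and 3.1.4). Visit windows (Section 6): ±2 days for Visits 3-8, and ± "7 days for Visits 9-14". Site doses are taken "after all study assessments for each visit have been completed" (Section 5.5.4), so gaps are counted from question to question.

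**The plan's own dose counts.** Section 5.5.4 gives 8 injections in the induction period and 18 in the open-label period. These reproduce: 4 doses × 2 = 8 (Weeks 12-15), and 9 doses × 2 = 18 (every four weeks, Weeks 16-48). From Week 12 there are therefore 4 + 9 = 13 dosing occasions, 7 of them at home.

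**Gaps as planned.** The range is the nominal gap ± the sum of the windows at its two ends.

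| Weeks | Nominal gap | Range with windows | Home doses in the gap |
|---|---|---|---|
| 12-16 | 4 weeks | 28 ± (2 + 7) = 19-37 days | 13, 14, 15 |
| 16-24 | 8 weeks | 56 ± (7 + 7) = 42-70 days | 20 |
| 24-32 | 8 weeks | 42-70 days | 28 |
| 32-40 | 8 weeks | 42-70 days | 36 |
| 40-48 | 8 weeks | 42-70 days | 44 |
| 48-52 | 4 weeks | 28 ± (7 + 7) = 14-42 days | none |

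The gaps sum to 40 weeks over 6 questions, a mean of 40/6 = 6.7 weeks. Of the 40 weeks, 4 × 8 = 32 (80%) lie in 8-week gaps.

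**Gaps if the call at each home dose also asks about AEs.** Questions fall at Weeks 13, 14, 15, 16, 20, 24, 28, 32, 36, 40, 44, 48 and 52. That is 13 questions with four gaps of 1 week and nine of 4 weeks (4 + 36 = 40), a mean of 40/13 = 3.1 weeks. The longest gap falls from 4 weeks to 1 in Weeks 12-16, and from 8 to 4 in Weeks 16-48.

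**What the call does not do.** It takes place around the time of dosing, so it mainly covers the period since the previous dose. A reaction to the Week 20 home dose would still first be asked about at Week 24, four weeks later, as now. A reaction to the Week 13 home dose would be asked about at Week 14 instead of Week 16.

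**The case against.** The strongest reply is that nothing is broken. The drug is given at its labelled dose in its approved indication. Subjects may volunteer events between visits (Section 7.1) and may be seen at any time, with AE assessment then required (Section 6). They are told to report new treatments (Section 5.5.8), and serious events are reported within 24 hours of the site learning of them (Section 7.2.2). The documents give no figure for how many events an extra question would bring in or bring forward. All of this stands, and it limits the point to an improvement.

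A reader might draw four stronger conclusions that the documents do not support:

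- *No safety contact outside visits is planned after Week 12.* Section 6 plans one in the 30 days after the last visit. The point holds for Weeks 12-52 only.
- *The switchers' four active doses in Weeks 12-15 go unchecked until Week 16.* The Week 12 dose is given at the site, and Section 6.5 asks for AE evaluation to be repeated after dosing. The doses with no scheduled AE contact afterwards are the home doses: three in Weeks 13-15 and one in each 8-week interval.
- *Only one call is made in Weeks 13-15.* The table text available for review shows a single mark there, but its columns are broken. Section 6.3 places calls at scheduled home dosing, and that reading is used here.
- *Every event first reported late is still summarised.* SAP Section 2.8.1 includes AEs by start date, so late reporting alone does not remove an event. However, non-serious AEs starting more than 7 days after the last dose are listed only.

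**Conclusion.** The point holds as a cheap improvement to safety follow-up that the sponsor could make. Between Weeks 12 and 52, scheduled AE questioning is 4 to 8 weeks apart (up to 70 days with windows), and no scheduled AE contact follows the seven home doses. Solicited questioning is delayed, not absent. The Week 12 comparison is untouched, and both arms follow the same schedule afterwards.

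The gain is a shorter recall period and earlier notice of events not volunteered. It is clearest in the switchers' induction, where weekly questioning would match what all subjects had in Weeks 0-4. For open-label home doses the wait from dose to first question stays at four weeks. The result assumes one call per home dose and nominal timing, since the protocol gives no window for the calls.

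**What to change.** Amend footnote P and Section 6.3 so that the call at each scheduled home dose also asks, non-directively as in Section 7.1, about AEs and SAEs since the last contact (including injection site reactions to the previous dose) and about new medications or vaccines. Mark the AE/SAE and concomitant-medication rows of Table 6-1 for those calls.

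No new contacts are needed. If the questions add 2-5 minutes (an assumption), seven calls add 14-35 minutes per subject. For 84 subjects that is 7 × 84 = 588 calls, or 588 × 2/60 = 19.6 to 588 × 5/60 = 49 staff hours if nobody discontinues. Footnote F already keeps the call record in source documents, so an eCRF entry is needed only when something is reported.

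The other costs are a written amendment with IRB/IEC approval (Section 11.1) and slightly more minor AEs recorded. If the change comes mid-study, AE ascertainment after Week 12 will differ before and after it, and the study report should say so.

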6.1 Information to be collected on screening failures

All subjects who sign informed consent but discontinue prior to randomization at Visit 2 are considered screening failures.

If a subject discontinues prior to randomization at Visit 2, the IRT must be notified about the discontinuation, and the primary reason for the screen failure should be entered in the Screening Phase Disposition eCRF.

The Screening Visit Date, Demography, Informed Consent, Inclusion/Exclusion Criteria, Subject Rescreening, and the Screening Phase Disposition eCRFs must be completed. The Adverse Event eCRF and a paper SAE form must be completed for any serious adverse event (SAE) that occurs during the screening period. Adverse events that are not SAEs will be followed by the Investigator and collected only in the source data. The Withdrawal of Informed Consent eCRF must be completed if consent was withdrawn during the Screening period before the subject was randomized.

